- Pain variables: Pain assessments will be conducted using a digital algometer to obtain the threshold for discomfort caused by pressure. Pain assessment will also be measured by the subject rating his/her pain level (range 0 to 10, with 0 being no pain and 10 being the worst pain imaginable) during hand placement into an ice water bath (cold pressor test).
- Other data/specimens: Muscle/brain oxygenation will be measured using a near infrared spectroscopy sensor that will be secured to the skin. End-tidal carbon dioxide will be measured

via capnograph. Muscle sympathetic nerve activity will be measured using microneurography. Compensatory reserve index will be estimated by recording photoplethysmography signals from the finger. Body mass will be measured using a scale. Venous blood samples will be collected from a peripheral arm vein. Urine specific gravity, drug screening and a pregnancy test will be determined from a urine sample collected at the beginning of the visit.

Volume Collected

- Urine: 1 – 2 ounces collected at the beginning of each visit
- Blood: A maximum of 100 mL of blood will be collected during visits 2 and 3.

De-identified blood samples may be sent to the U.S. Army Institute of Surgical Research (USAISR) at Ft. Sam Houston, Texas. No subject information will be sent with the blood samples and no subject information will be exchanged with USAISR.

Chronological Detail

The times listed below are approximate and listed in order, from subject arrival.

All Specific Aims – 3 visits/subject (preliminary session: ~1 hour; 2 experimental visits: up to ~5.5 hours each; total time ~12 hours):

Visit 1 (preliminary visit) (~1 h)

- 60 min: consent form, HIPAA authorization, W-9 tax form, and self-reported medical history; resting blood pressure, 12 lead ECG, pregnancy test, if applicable, procedure familiarization, and drug screen; instruction sheet for experimental visits will be provided

Visits 2 and 3 (experimental visits) – 2 visits (~5.5 hours each visit)

- 15 min: urine sample (pregnancy test, if applicable), body mass measurement, instrumentation with ECG, blood pressure cuff
- 90 min: supine position assumed, insertion of an IV catheter in a vein of the arm, and muscle sympathetic nerve activity signal obtained
- 30 min: baseline data collection followed by pain assessments (cold pressor test and pressure algometry)

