- 45 min: drug administration (placebo or morphine) followed by progressive LBNP to the onset of syncopal signs/symptoms (blood pressure, cardiac output, forearm blood flow, cerebral blood flow, pulse oximeter, blood samples collected; heart rate, muscle sympathetic nerve activity measured continuously)
- Up to 60 min: recovery
- 30 min: pain assessments (cold pressor test and pressure algometry)
- Up to 60 min: recovery followed by pain assessments (cold pressor test and pressure algometry)

Primary Outcome Variables

The primary outcome variable will be the ability to tolerate the LBNP challenge prior to the onset of signs and symptoms associated with ensuing syncope.

Study Endpoints

Data collection will end when 30 subjects (15 male and 15 female) have completed the experimental protocol.

Sample Size Justification

No study has evaluated the effects of analgesics on LBNP tolerance in humans. The power and sample size estimates are based on findings from [name] laboratory showing reduced LBNP tolerance

Crandall_Morphine_Protocol_updated

Version <insert version number and date>

in the heat-stressed individuals (15). In that study heat stressed reduced LBNP tolerance by ~70% (997 cumulative stress index units to 303 cumulative stress index units; $P < 0.001$). Though we expect the analgesics to likewise reduce LBNP tolerance, we do not anticipate as large of a reduction as that observed with heat stress. Thus, the sample size calculation was based upon an anticipated reduction in LBNP tolerance of half that seen with heat stress, i.e., ~35% reduction in the cumulative stress index. Given this anticipated outcome, coupled with the associated variances observed in that study (15), we anticipate 15 subjects per drug trial will be sufficient to address the primary hypothesis that the administered analgesic reduces tolerance to a simulated hemorrhagic insult, with a study power=0.80 at an adjusted $\alpha=0.015$ to account for comparisons between drugs. That value was inflated to 30 subjects in total (15 male and 15 female) to permit a comparison in the primary responses between sexes for each of the administered drugs. That said, interim power analyses will be performed, with the number of required subjects adjusted based upon the variance of the obtained data.

5. Sub-Study Procedures:

Not applicable

6. Criteria for Inclusion of Subjects:

- 18-45 years of age
- Healthy
- Body mass index less than 35 kg/m²
- Body mass greater than or equal to 60 kg

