The doses of the drugs are expected to cause analgesia, but with the subject remaining conscious and responsive to verbal commands. These drugs are routinely administered for pain control in the absence of significant sedation. Nevertheless, if after the first or second administration of the selected analgesic the subject is not responding appropriately to verbal commands (e.g., is excessively sleepy/sedated) or experiences any related adverse responses to the administered drug, the trial will be cancelled for that subject.

Subjects who, during the study, manifest a new onset, previously hidden or unknown cardiovascular, neurological or metabolic disease/illness will be removed from the study.

The study will be stopped immediately for safety if a serious, unexpected problem or adverse event occurs. The entire project will be terminated if this event is determined to place future participants at undue risk.

12. Procedures to Maintain Confidentiality:

- 1) Information will be given to the principal investigator and his staff only.
- 2) Information concerning subject's medical histories will be furnished by the subjects to the staff.
- 3) This information will be used to determine qualification for participation in the investigation.
- 4) Personal information will remain in the subject's study chart and will not be released in any form to others unless permitted by the subject.
- 5) The consenting process for each subject will be conducted in a private room.
- 6) No subject will be identified by name or initials outside the laboratory records. All computer records will be coded and will not include the subject's name. All coded computer records will be saved on password protected computer systems and data files are maintained on a secure server.
- 7) The signed consent form will be kept on file in the subject's laboratory chart. Paper records of experiments and copies of executed consent forms will be locked in cabinets located in the research nurse's office which is locked whenever the nurse is not present.
- 8) The urine specimens collected for the drug screening will not be labeled and will be directly handed to a member of the study team by the participant (making it anonymous). There is no processing required as the results appear on the side of the specimen collection cup.

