With regard to those outside the military, the experiments outlined in this application will determine the effect of currently employed pain medications on tolerance to a simulated hemorrhage in humans. These data will identify the pain medication that least compromises a human's ability to tolerate such an insult, thereby providing critical information to the pre-hospital medics on which pain medication should be employed for such an injury. Obtaining these data will be the first step in the continuum of research that will culminate in an increased understanding of the link between analgesia and hemorrhage. Moreover, the proposed work is particularly unique in that it will be the first investigation conducted in conscious humans to identify the optimal pain medication that will only minimally impair compensatory responses to a hemorrhagic injury, and thus the ability to "survive" that insult. This information will be valuable to both the military and civilian populations as it will improve pre-hospital care of the hemorrhaging victim.

14. Biostatistics:

The primary outcome variables are tolerance to the LBNP challenge with and without analgesic administration. The effects of morphine on LBNP tolerance, as well as pain assessment, will be evaluated via a paired T-test (i.e., placebo versus drug).

The effects of the administered drugs on hemodynamic and autonomic responses to each LBNP stage will be compared via two way mixed model ANOVA design, with main factors of drug and LBNP level (analyzed both by stage and by % completion of the entire LBNP protocol to pre-syncope). A significant interaction from those ANOVAs will be further explored via pairwise multiple comparison analyses.

Analysis assumptions will be carefully evaluated, data transformations considered, and Bonferroni-Hochberg will be used to adjust for multiple testing as appropriate.

15. References

1. Bellamy RF. The causes of death in conventional land warfare: implications for combat casualty care research. *Mil Med.* 1984 Feb;149(2):55-62.

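### The paired t-test for pain gives the pre-drug pain value no role; regressing on the pre-drug visit difference is a cheap improvement that gains precision at n=30 if rho exceeds about 0.19

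*Combined protocol and SAP*

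**What the plan says.** The visit schedule (Chronological Detail, Visits 2 and 3) places one set of pain measurements before the drug: "baseline data collection followed by pain assessments (cold pressor test and pressure algometry". The drug and the LBNP challenge follow: "45 min: drug administration (placebo or morphine) followed by progressive LBNP to the onset of syncopal signs/symptoms". After a recovery period comes the first post-drug set, "30 min: pain assessments (cold pressor test and pressure algometry", and later the second, "Up to 60 min: recovery followed by pain assessments (cold pressor test and pressure algometry". Both measures, the algometer threshold and the 0-10 cold pressor rating, are therefore taken three times per visit, at a placebo visit and a morphine visit in the same subject.

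Section 14 (Biostatistics) gives one sentence on how pain is analysed: "The effects of morphine on LBNP tolerance, as well as pain assessment, will be evaluated via a paired T-test (i.e., placebo versus drug". It does not say which post-drug assessment is compared. It also does not say whether the pre-drug value is subtracted, adjusted for or set aside. The mixed-model ANOVA in the same section covers hemodynamic and autonomic responses by LBNP level, not pain.

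Collection ends at 30 completers (Study Endpoints). Section 11 says of the doses: "The doses of the drugs are expected to cause analgesia". The pain assessments are where that expectation can be checked in these subjects.

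**The concern.** Pairing removes stable differences between subjects. It does not remove shifts within a subject from one visit day to the other. If a subject is more pain-sensitive on one day, both the pre-drug and the post-drug readings of that day may carry the shift. A test on post-drug values alone then counts the shift as error, although a measurement already collected could explain part of it.

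A paired t-test on change from pre-drug also fits the sentence in Section 14. Subtracting the full pre-drug value helps only when the two visit differences are strongly correlated, and adds noise otherwise. Neither reading uses the pre-drug value efficiently when its predictive strength is unknown.

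What is at stake is precision in a secondary comparison: how sharply the study can show that morphine was analgesic here. Nothing in the LBNP tolerance comparison depends on it.

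**Working it through.** **Plan's own figure.** The documents give no sample size or power for pain, so there is nothing to reproduce. The 15 subjects, inflated to 30, refer to LBNP tolerance and rest on variances from a cited study that are not shown.

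**Inputs.** n = 30 pairs (Study Endpoints). For each subject, Dpre and Dpost are the differences between the placebo and morphine visits before the drug and at one post-drug assessment. Rho is their correlation, and m is the mean of Dpre in units of its SD. The documents give neither rho nor m, so both are varied. Also assumed: normal data, equal variances of Dpre and Dpost unless stated, and a two-sided 5% test.

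**Variance relative to the post-drug-only paired t-test:**
- Regression of Dpost on Dpre, testing the intercept, with m = 0: (1 − rho²)(n − 2)/(n − 3), on average over samples.
- Change score: 2(1 − rho).

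**Cost and break-even at n = 30, m = 0.** At rho = 0 the factor is 28/27 = 1.037, an average cost of 3.7% in variance. Regression breaks even when rho² = 1/(n − 2) = 1/28, so rho = 0.189. The change score breaks even with the post-drug-only test at 2(1 − rho) = 1, so rho = 0.5. Regression beats the change score while (1 + rho)(28/27) < 2, that is for rho below 0.93.

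| rho (assumed) | regression | change score |
|---|---|---|
| 0 | 1.04 | 2.00 |
| 0.3 | 0.94 | 1.40 |
| 0.5 | 0.78 | 1.00 |
| 0.8 | 0.37 | 0.40 |

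Simulation with 200,000 trials per value gave regression ratios of 1.036, 0.999, 0.945 and 0.778 at rho 0, 0.189, 0.3 and 0.5, in agreement with the formula.

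**If m is not zero.** At rho = 0 the factor becomes 1 + (1 + n·m²)/(n − 3).
- m = 0.2: 1 + (1 + 1.2)/27 = 1.081; break-even rho = √(1 − 1/1.081) = 0.27.
- m = 0.3: 1 + (1 + 2.7)/27 = 1.137; break-even 0.35.

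**If response to morphine varies between subjects.** Take single-measurement variance 1, within-visit correlation 0.9, between-visit correlation 0.5 and response variance 0.5. Then rho = 0.8/√(1 × 1.5) = 0.65 and the ratio is (1 − 0.427)(28/27) = 0.59. With no such variation the same correlations give rho = 0.8 and 0.37. Equal variances therefore flatter the regression.

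**Power at n = 30, m = 0 (noncentral t; 29 df for the paired test, 28 for the regression).** The effect is the mean of Dpost over its SD; 0.53 is the value at which the post-drug-only test has 80% power.

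| effect | post-drug-only | rho 0 | 0.3 | 0.5 | 0.8 |
|---|---|---|---|---|---|
| 0.3 | 36% | 34% | 37% | 44% | 74% |
| 0.53 | 80% | 78% | 82% | 89% | >99% |
| 0.8 | 99% | 99% | 99% | >99% | >99% |

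**Type I error.** In simulation the regression held 4.8-5.1% for normal data and 4.8-5.3% for values rounded and clipped to a 0-10 scale.

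**The case against.** The strongest reply is that this is optional. The paired t-test is valid, neither Specific Aim states a pain hypothesis, no power is claimed for pain, and the benefit turns on a correlation nobody has reported. At rho 0.3 the gain is about two points of power (80% to 82% at effect 0.53). All of that stands, and it sets the severity at low.

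Three stronger readings are tempting, and the documents do not support them.

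- A reader might take 4% as the worst case. It is the average cost at rho = 0 when the mean pre-drug difference between visits is zero. That mean is expected with balanced visit order and no carry-over, but the available text does not state the order. A mean of 0.2 or 0.3 SD raises the cost to 8% or 14%, and a single sample with a large chance imbalance can cost more.
- A reader might apply the argument to 15 subjects of one sex, where break-even is √(1/13) = 0.28 and the cost 1/12 = 8%. The plan compares the sexes on the primary responses; it schedules no within-sex pain analysis. The statement that "interim power analyses will be performed, with the number of required subjects adjusted based upon the variance of the obtained data" could move n either way and names no such figure. Results at n = 15 are hypothetical.
- A reader might infer that the plan discards the pre-drug value. Section 14 is silent; it excludes nothing, and a change-score reading is open. That reading does not remove the point, because with equal variances it loses to the post-drug-only test below rho 0.5 and to regression below rho 0.93.

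It is also fair to say that normal-theory precision figures are only approximate for a bounded 0-10 rating. Section 14 already commits to checking assumptions and considering transformations.

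**Conclusion.** The point holds as a low-severity improvement to a secondary analysis. The planned test is not wrong; it is silent about a covariate already in hand. Regression risks about 1.5 points of power at effect 0.53 if the pre-drug difference is uninformative, and gains about 9 points if rho is 0.5. With a large effect (0.8) the choice makes no practical difference. These figures rest on n = 30, a mean pre-drug difference of zero, approximate normality and equal variances. The size of any gain stays unknown because rho is unknown.

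The estimand should be stated. The intercept is the drug effect at zero pre-drug difference. The paired t-test targets that intercept plus the slope times the mean pre-drug difference, so the two agree only if that mean, or the slope, is zero.

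**What to change.** Add to Section 14, for each pain measure: 'The within-subject placebo-morphine difference at [one named post-drug assessment] will be regressed on the uncentred pre-drug difference between the same two visits, and the intercept, the drug effect at zero pre-drug difference, will be tested. The other post-drug assessment will be analysed in the same way as supportive.'

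The sponsor should choose the main assessment before analysis and give the reason. By the approximate schedule, the first begins within about 45 + 60 = 105 minutes of the start of the drug and LBNP block, and the second within about 45 + 60 + 30 + 60 = 195 minutes. Naming one is worthwhile whatever rho proves to be, since the present sentence leaves the choice open. The visit order should be stated alongside, because the zero-mean condition depends on it.

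The cost is a few sentences, no new data and one degree of freedom (28 instead of 29), plus the average variance cost above if the pre-drug difference turns out to be uninformative.

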We propose that if sufficient doses of commonly employed analgesics are administered to humans, otherwise appropriate cardiovascular responses to the hemorrhagic insult will be suppressed, thereby reducing the ability of the individual to tolerate that insult. That said, the effects of analgesic doses of such agents (i.e., doses that are recommended for the pre-hospital setting) on physiological responses necessary to preserve tolerance to a hemorrhagic insult in humans is entirely unknown. Moreover, the aforementioned guidelines by the CoTCCC for condition-specific analgesics are not based upon hypothesis driven scientific evidence in humans, but rather primarily from fully anesthetized animals. Thus, the applicability of that research to a soldier experiencing a hemorrhagic injury is questionable and remains a significant gap in the knowledgebase.

3. Concise Summary of Project:

Three separate protocols, one for each analgesic—fentanyl, morphine, and ketamine will be employed.

Three laboratory visits will be required for this protocol.

The first visit will begin with the consenting process. Should the interested subject qualify and agree to participate in the study, he/she will undergo two separate experimental visits (placebo and morphine) each conducted on a different day. The protocol for each experimental visit is identical. After instrumentation, subjects will rest quietly followed by baseline data collection and then assessments of pain (via algometer and the cold pressor test). Subjects will then receive the drug along with the progressive lower-body negative pressure (LBNP). This will be followed by a recording of post-drug data and re-performance of the pain assessments. For the placebo trial, saline (sodium chloride 0.9% or if unavailable, 5% dextrose in water) will be administered where “Drug Administration” is indicated above. The enrolled subject will be required to complete both placebo and morphine conditions.

- End tidal carbon dioxide: capnography
- Oxygen saturation: pulse oximetry
- Muscle and brain oxygen saturation: near infrared spectroscopy
- Compensatory reserve index: photoplethysmography of finger blood flow
- Body mass
- Venous catheter and blood samples: see list below
- Saline infusion (via venous catheter)
- Subjective pain reporting to pain assessments (cold pressor test)
- Threshold for pressure discomfort: digital algometer
- Urine specific gravity
- Drug screening
- Pregnancy test

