- Speak English

7. Criteria for Exclusion of Subjects:

- Subjects who have cardiac, respiratory, neurological and/or metabolic illnesses
- Any known history of renal or hepatic insufficiency/disease
- Pregnancy or breast feeding
- Current smokers, as well as individuals who regularly smoked within the past 3 years
- Positive urine drug screen
- Currently taking pain modifying medication(s)

Although this study requires relatively uncomplicated procedures, inclusion of non-English speaking subjects would compromise subject safety. Consequently, it is imperative that the research and medical staff are able to communicate instantly and effectively with subjects, without the need of a translator. Therefore, the investigators feel that inclusion of non-English speakers would markedly and unnecessarily increase the risk to those participants.

8. Sources of Research Material:

“Research Material” (i.e., data) will be obtained from healthy human subjects. See section 4: Study Procedures for a list of data that will be obtained.

Healthy individuals: Complete datasets will be obtained from a total of 30 individuals (15 male and 15 female). Subjects will be 18-45 years old.

Due to screening failures (e.g., not determined to be healthy, use of medication, etc.), we anticipate 50 subjects will be consented to achieve the desired 30 subjects.

9. Recruitment Methods and Consenting Process:

Crandall_Morphine_Protocol_updated

Version <insert version number and date>

Page 6 of 12

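### Section 14's paired t-test has no period term, although placebo and morphine are given on different days; a two-period crossover model is a cheap improvement

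*Combined protocol and SAP*

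**What the plan says.** Section 3 (Concise Summary of Project) gives the design: after consent, "he/she will undergo two separate experimental visits (placebo and morphine) each conducted on a different day". Every enrolled subject must complete both.

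Section 14 (Biostatistics) gives the analysis: "The effects of morphine on LBNP tolerance, as well as pain assessment, will be evaluated via a paired T-test (i.e., placebo versus drug". Its only other model, for hemodynamic and autonomic responses, is a two-way mixed ANOVA "with main factors of drug and LBNP level". It then adds "Analysis assumptions will be carefully evaluated, data transformations considered", without naming a check for visit or order. None of these analyses contains period, order or sex.

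The Sample Size Justification derives 15 subjects for the primary hypothesis and continues: "That value was inflated to 30 subjects in total (15 male and 15 female) to permit a comparison in the primary responses between sexes". It also allows interim power analyses, "with the number of required subjects adjusted based upon the variance of the obtained data". Section 8 counts completers: "Complete datasets will be obtained from a total of 30 individuals (15 male and 15 female".

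The supplied text does not say how visit order is assigned. Section 8 points elsewhere for procedures ("See section 4: Study Procedures for a list of data that will be obtained"), and the text available runs from Section 3 into a list of measurements with no Section 4 heading. An order rule may therefore exist in text that is not available here.

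**The concern.** Placebo and morphine are compared across two visits. If LBNP tolerance shifts between the first and second visit for any reason unrelated to the drug, that shift raises the morphine-minus-placebo difference in subjects who take one order and lowers it in those who take the other. A paired t-test treats the shift as noise when the orders are equal in number. When they are not, part of it enters the estimate. The pain assessments, named in the same sentence of Section 14, and the drug-by-LBNP-level model are open to the same effect.

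The sex comparison is the stated reason for going from 15 to 30 subjects, yet Section 14 names no test for it. A difference in order split between men and women would enter that comparison as well. One model can cover both needs.

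**Working it through.** **The plan's own figure.** The reference means are 997 and 303 CSI units, a fall of (997 − 303)/997 = 69.6%; half of that is about 35%, and 0.35 × 997 = 349 units. The stated n = 15 cannot be reproduced, because no SD is given and the sidedness of α = 0.015 is not stated. Working backwards with the noncentral t (n = 15, power 0.80):
- two-sided: standardised effect 0.947, so SD = 349/0.947 = 368;
- one-sided: standardised effect 0.851, so SD = 349/0.851 = 410.

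The normal approximation gives 413 and 449. I use 368 and two-sided α = 0.015.

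**Assumed inputs.** The documents give no visit effect. I take a first-to-second-visit change v of 50, 100 or 150 units (5% to 15% of 997). The 200-unit drug effect below is likewise only an illustration of an effect smaller than planned.

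**Model.** The difference for subject i is Dᵢ = effect + v for one order and effect − v for the other, plus error with SD 368; n = 30. Let p be the share of subjects in one order.
- Bias of the paired contrast: v(2p − 1). At 15/15 it is 0. At 20/10 it is v/3, or 17/33/50 units.
- Expected variance seen by the paired t-test at 15/15: 368² + v² × 30/29, giving SD 372/382/399. At v = 150 the SD is inflated by 8% (399/368 = 1.08). With SD 410 the same sum gives √(1 + 23,276/168,100) = 1.07.
- Period-adjusted estimate: the mean of the two order-group means, with SE = (368/2) × √(1/n₁ + 1/n₂). This is 67 at 15/15 and 71 at 20/10.

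**Results** (simulation, at least 50,000 runs per entry; nominal rate 1.5%):

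| | v = 50 | v = 100 | v = 150 | with period term |
|---|---|---|---|---|
| False positives, paired t, 15/15 | 1.4% | 1.2% | 0.9% | about 1.5% |
| False positives, paired t, 18/12 | 1.5% | 1.6% | 1.6% | about 1.5% |
| False positives, paired t, 20/10 | 1.7% | 2.2% | 3.0% | about 1.5% |
| Power at 349 units, paired t, 15/15 | 0.993 | 0.991 | 0.988 | 0.993 |
| Power at 200 units, paired t, 15/15 | 0.65 | 0.62 | 0.58 | 0.65 |

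Repeat runs move the last digit by one (2.9% for 3.0%, 0.57 for 0.58).

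**How likely is an uneven split?** Under unrestricted 1:1 assignment of 30 subjects, the binomial probability of 20/10 or worse is 0.099. The 20/10 row is conditional on that split. Averaged over all splits that such assignment can produce, the paired t-test rejects about 1.5% of the time, which is nominal.

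**Sex comparison.** The bias in men minus women is 2v(p_men − p_women). At 10/5 in men and 5/10 in women it is 2v/3, or 33/67/100 units, against an SE of 368 × √(2/15) = 134. This too is conditional on a poor split.

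**Price of the period term.** With no visit effect, power at 349 units is 0.993 with the term at 15/15 (0.994 without it), 0.991 at 18/12 and 0.986 at 20/10. At 200 units and 20/10 the noncentrality is 200/71.3 = 2.80 on 28 df, and power is about 0.59 against 0.65 for the paired t-test.

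**The case against.** The strongest reply is that a paired t-test under randomised 1:1 order is valid. Its error rate is nominal on average and conservative when order is balanced, and at the planned effect the period term gains at most half a percentage point of power. The size rests on an assumed visit effect and a back-solved SD. Visit 1 includes some familiarisation with the procedures, which may reduce any first-visit effect. All of this stands, and it is why the point is an improvement and not a fault in the primary test.

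Three stronger readings are tempting, and the documents do not support them.
- **Visit order is not randomised.** The text is silent, but the procedures section appears to be incomplete here, so silence is not evidence. If all 30 subjects shared one order, the false-positive rate would be 4%/15%/38% for v = 50/100/150 and a period term could not help. Nothing in the documents points to that.
- **15 men and 15 women cannot be balanced.** No whole-number split balances order exactly for both the overall and the sex contrast. The leftover is only v/15 in one or 2v/15 in the other: at v = 150, 10 units against an SE of 67, or 20 against 134, about 15% of an SE. It also applies only to the stated target, which the plan allows to change.
- **Dropout will unbalance the order.** Section 11 lists attrition for monitoring and allows a subject's trial to be cancelled after dosing. Since both conditions are required, a subject cancelled at the morphine visit is a non-completer in either order. No order-dependent loss is documented.

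Section 17-style emphasis on sex should not be overread either: the benefits section (Section 13) describes the sex question as exploratory. Even so, it is the stated reason for doubling the sample, and it has no named analysis.

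**Conclusion.** The point holds as a low-cost improvement. With order randomised or balanced, the planned test remains valid but loses some efficiency if tolerance changes between visits. The loss is negligible at 349 units. At 200 units it reaches about 7 percentage points of power for v = 150. With an uneven realised order, a fraction of the visit change biases that trial's estimate, by one third at 20/10 with a conditional false-positive rate of 1.7% to 3.0%, although the rate averaged over 1:1 assignment stays nominal. A period term restores about 1.5% at every two-order split examined.

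These sizes assume SD 368, v of 50 to 150 units, an additive visit effect common to all subjects, and no carry-over, which a period term does not address. The absence of a period term and of a sex test from Section 14 does not depend on the missing text. Any larger harm does.

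**What to change.** In Section 14:
1. Replace the paired t-test, for LBNP tolerance and for the pain assessments, with a two-period crossover model: condition and period as fixed effects, subject as random.
2. Add period to the drug-by-LBNP-level mixed model.
3. For the sex comparison, add sex and condition × sex to the model in item 1 and name the interaction as the test.
4. Report the order split by sex among completers.

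The cost is a few lines of text and one degree of freedom for period. If order turns out uneven and there is no visit effect, the standard error is slightly larger (71 against 67 at 20/10). No extra subjects, visits or measurements are needed. Fix the wording before the outcome data are analysed; the documents do not show how far accrual has gone.

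As a query only, ask the sponsor to confirm that visit order is randomised 1:1 within sex. The rule may already be in Section 4, and no model can separate drug from visit if every subject has the same order.
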